2.0 Objectives

2.1 *Describe the purpose, specific aims, or objectives of this study:*

Purpose: To examine the effects of filter ventilation and e-cigarette restrictions (on flavor and nicotine concentration) on cigarette demand and the corresponding degree to which e-cigarettes and other non-combustible tobacco products substitute for cigarettes.

2.2 State the hypotheses to be tested:

This study is designed to better understand the effect of possible e-cigarette restrictions. We hypothesize that e-cigarette restrictions will decrease substitution for e-cigarettes, with the smallest degree of substitution when both flavors and nicotine concentration are restricted.

3.0 Background

3.1 Summarize the relevant prior research on this topic and gaps in current knowledge within the field of study:

The Food and Drug Administration (FDA) was granted authority in 2009 to establish tobacco product standards if those standards are reasonably expected to benefit the public health. One product feature that could be changed is cigarette filter ventilation. A recent review examined the effects of cigarette filter ventilation and concluded that filter ventilation, by changing how a cigarette burns, yields more mutagens and carcinogens, and results in greater puff volume and possibly depth of inhalation, which has led to increases in peripheral lung adenocarcinomas (1). This, along with the ability to manipulate systemic levels of nicotine by altering smoking behavior, as well as misconceptions about the lower toxicity of filter ventilation, may have also contributed to the use, appeal, and abuse liability of ventilated cigarettes. The extent to which commercial cigarettes are ventilated vary substantially in the market by brand, ranging from 0 to 80%. However, smokers compensate for the lower nicotine yields associated with higher ventilation by varying their puffing behavior, number of cigarettes per day, and blocking some portion of the ventilation holes. This compensatory behavior exposes smokers to more tobacco smoke constituents than would be indicated by machine smoking tests. Regulatory action that reduces or eliminates cigarette ventilation would not only reduce exposure to smoke constituents by increasing nicotine yield per cigarette, but also change the smoker's experience, likely resulting in harsher taste that may be proportional to the ventilation in a given cigarette brand. The potentially large effect on taste and preference corresponding to cigarette ventilation could alter the appeal and abuse liability of these products and could inform regulatory actions. However, eliminating filter ventilation raises a variety of questions that constitute a gap in our knowledge and must be answered to assess the potential for adverse unintended consequences of removing filter ventilation. We will explore these questions within a behavioral economic framework.

Behavioral economic demand analyses can be used to understand the level of motivation to consume a product on either an individual or small group level, including cigarettes (2,3). This level of analysis allows for experimental manipulations to be made on variables of interest. By quantifying how consumption decreases as costs increase to obtain and consume a product, important indices of demand are obtained. These indices can be grouped into two main measures of consumption, demand intensity and demand

20-008 Effects of Cigarette and E-cigarette flavors on Substitutability in the Experimental Tobacco Marketplace

elasticity, which are associated with use level and dependence severity (3,4,5,6). Demand intensity is the amount of the commodity consumed when available at very low cost (approaching free), and demand elasticity quantifies the degree to which the individual is willing to increase monetary or effort-based expenditures to maintain the same level of consumption as costs increase. Elasticity of demand has been shown to be a characteristic of the drug itself and independent of drug dose for many drugs including nicotine (2,7,8). While drug demand plotted as a function of unit price has been often shown to be a function of the total drug consumed, some of our prior research with cigarette demand calls this conclusion into question. A prior study we conducted (9) compared conventional cigarettes to denicotinized cigarettes. We found that, if these denicotinized cigarettes were the only tobacco product available, the denicotinized cigarettes had comparable demand to nicotinized cigarettes. If both were available, however, participants preferred the nicotinized cigarettes. This suggests that cigarette demand is not strictly regulated by nicotine dose, and that there is substantial abuse liability associated with other aspects of cigarettes (e.g., sensory components) apart from any nicotine content. Relevant to this point and the current application, we conducted a pilot study, where conventional ventilated cigarette smokers purchased either their usual cigarettes (ventilated) or their usual cigarettes with the filter vents blocked. When each cigarette type was available alone in separate sessions, demand for both products was very similar. However, in a separate session in which both cigarette types were available concurrently at equivalent unit prices, ventilated cigarettes were clearly preferred at all prices. These findings suggest that to fully understand the abuse liability of cigarettes will require that they are studied in contexts where other products are available (e.g., substitution).

Substitution is defined as an increase in the consumption of a constant-priced product while the cost of a different commodity is increased. For example, we have shown that as the price of conventional cigarettes is increased and its consumption decreased, the consumption of nicotine gum increased even though its price remained constant (10). Substitution defines one end of a continuum of interactions between two commodities. At the other end of that continuum, commodities can also function as complements. Complementarity refers to the decreased consumption of a constant-priced product in response to an increase in the price of a different commodity. For example, the research team has previously shown that as the price of cigarettes increased, consumption of coffee decreased even though its price remained constant (11). Between these two extremes is independence, which occurs when changes in the price of one commodity have little or no effect on consumption of another commodity where price has remained unchanged. Substitution, complementarity, and independence are measured by cross-price elasticity of demand and are represented by values that are positive, negative, or near zero, respectively. Studies to date have almost exclusively examined only pairs of products and, in even fewer cases, three concurrently available commodities. For example, in one of our studies smokers had access to conventional cigarettes, denicotinized cigarettes, and nicotine gum¹³. When the price of conventional cigarettes increased, consumption of both denicotinized cigarettes and nicotine gum increased even though their prices were fixed. Thus, denicotinized cigarettes and nicotine gum functioned as substitutes for conventional cigarettes. Indeed, by concurrently using both

20-008 Effects of Cigarette and E-cigarette flavors on Substitutability in the Experimental Tobacco Marketplace

products, the smoker could reproduce both the central and sensory effects of standard cigarettes by consuming the denicotinized cigarette (i.e., sensory effects) and nicotine gum (i.e., central effects). Importantly, denicotinized cigarettes functioned as a better substitute than gum (the use of denicotinized cigarettes increased the most). This effect could not have been predicted from the individual demand curves with these commodities. Only when they were measured together did these complex interactions emerge. Lastly, in this experiment consumption of conventional cigarettes was greatest when it was the only available product, and was least when denicotinized cigarettes or both alternatives were available. This finding demonstrates that cigarette demand was altered by the presence of alternative products and that under some conditions multiple products will be used concurrently. However, this and similar studies are constrained by arbitrary circumstances of the laboratory, such as required nicotine deprivation, constrained consumption of a product (e.g., 1 cigarette puff per self-administration), long and numerous sessions (e.g., one, 3-hour session for each price examined). As such, these methods cannot and do not come close to replicating the ever more complex tobacco marketplace and underscore the gap in the understanding of how to examine these relationships among a large number of products that approximate the real world.

To address this methodological gap and to inform how various products may interact, we have developed and tested a novel method called the Experimental Tobacco Marketplace (ETM). The ETM is a systematic extension of similar marketplace methods used with other consumer products (e.g., food marketplaces used in obesity and other nutrition-related research). In experimental marketplaces, multiple products are available and the experimenter controls the prices for each. These marketplaces can be either physical or virtual stores (similar to online retailers) and permit the examination of price effects and an assessment of degree of substitution or complementarity in consumer behavior under conditions that approximate naturalistic settings. One such study (12) examined foods purchased by mothers when less healthy foods were taxed (increased price) and healthier foods were subsidized (decreased price). These authors found that taxing less healthy food reduced caloric intake and proportion of calories from fat, while increasing the amount of protein consumed. Alternatively, subsidizing healthier foods did not change the macronutrient profile of foods purchased while increasing energy intake. In a review of this emerging area of nutritional research, Epstein and colleagues noted that “price changes modify purchases of targeted foods, but research on the overall nutritional quality of purchases is mixed because of substitution effects” (p. 789; (13)). This statement suggests the importance of exploring regulatory options in complex marketplaces. The ETM developed by the investigative team is similar to an online store, that displays pictures, information, and prices for several tobacco/nicotine products. In a recent study of ours (14), smokers were endowed with an amount of money comparable to their weekly tobacco purchases. They then made tobacco product purchasing decisions while the price of conventional cigarettes was varied and the price of 5 other tobacco products remained constant. Purchasing decisions from one, randomly selected cigarette price was actualized and smokers were provided the products purchased and any unspent account balance. Smokers returned one week later to report tobacco/nicotine use and return unused products for a refund. Cigarette consumption decreased as a function of price. As the price of cigarettes increased, consumption of snus, electronic cigarettes, and

The Experimental Tobacco Marketplace (ETM) [6], a novel method recently developed, permits estimates of the effects of new policies and products on consumption and substitution in the tobacco marketplace. This methodology places the mix of products, prices, and specific policies under experimental control so as to provide estimates of novel policies obtained under conditions that simulate "real world" circumstances. This approach provides insight into how a given policy may alter consumption, preferences, and substitution among tobacco products. As part of this grant, one previous study has examined the effect of removing filter ventilation on nicotine product consumption. Preliminary analysis shows that exposure to unventilated cigarettes might decrease demand for ventilated cigarettes and increase substitution for unventilated cigarettes. The manuscript is currently in preparation.

3.3 Based on the existing literature, provide the scientific or scholarly rationale for and significance of your research and how will it add to existing knowledge:

20-008 Effects of Cigarette and E-cigarette flavors on Substitutability in the Experimental Tobacco Marketplace

No study to date has experimentally examined the effects of e-cigarette restrictions on demand for unventilated and ventilated cigarettes and substitution for other tobacco products. The rationale for this specific proposal is to explore prospectively the possible consequences of e-cigarette restrictions on consumption and substitution with tobacco products among ventilated and unventilated smokers. The results might inform tobacco control policies.

4.0 Study Endpoints

4.1 *Describe the primary and secondary **study** endpoints. See links below for discussion of study endpoints and how they may differ from study objectives. These are most common in clinical trials but are sometimes applicable to other types of biomedical research, as well as social, behavioral, or educational research. See link below for a discussion.*

https://docs.google.com/document/d/1Wocz7K7a0hCQJPPO_khh511SQjhGDDGHzcOPRHR5Tw/edit?usp=sharing

Substitutability: all groups will be compared to assess whether substitutability with tobacco products occurs as a function of different flavor and nicotine restrictions and cigarette price.

4.2 *Describe any primary or secondary **safety** endpoints. These should be included for all studies that are greater than minimal risk. (Minimal risk: The probability and magnitude of harm or discomfort anticipated in the research that are not greater in and of themselves than those ordinarily encountered in daily life or during the performance of routine physical or psychological examinations or tests.):*

This study will recruit adults who regularly smoke cigarettes. This study's procedures are not designed to increase daily nicotine use and we do not anticipate any increased risk to participants directly from this study.

5.0 Study Design and Statistical Analysis Plan

5.1 *Describe the basic study design/approach (e.g., qualitative study using five focus groups of first year students to describe assimilation into the university community; randomized controlled trial of a behavioral change intervention to increase dietary intake of whole grains; pre- post-test evaluation of new pedagogical techniques to improve adult literacy):*

In a one-session study, participants will complete assessments and purchase tobacco products in a hypothetical ETM. All participants will complete four ETM conditions, all of which include five trials assessing different prices of their preferred cigarette. In each

20-008 Effects of Cigarette and E-cigarette flavors on Substitutability in the Experimental Tobacco Marketplace

ETM condition, participants will purchase tobacco/nicotine products for a 7-day period. Unventilated and ventilated cigarettes, as well as a range of other products (i.e., lozenges, snus, gums, and dip), will be always available. Availability of e-cigarettes will vary according to the following conditions:

- A) Nicotine restricted and flavor restricted
- B) Nicotine unrestricted and flavor restricted
- C) Nicotine restricted and flavor unrestricted
- D) Nicotine unrestricted and flavor unrestricted

Participants will be exposed to these restriction conditions across purchasing scenarios in a counterbalanced order.

5.2 *Describe corresponding data analysis plan/approach (e.g., content analysis of focus group transcripts; descriptive analysis followed by linear regression modeling; nonparametric analysis of pre- and post-test measures):*

The analysis of each group will assess whether substitutability occurs as a function of different e-cigarette conditions. The relationship between consumption and condition will be modeled according to:

$$y_{ij} = \mu + \alpha_i + \tau_j + \varepsilon_{ij},$$

where y_{ij} represents the average log consumption for the i th e-cigarette restriction and the j th subject, α_i is the effect of the i th condition on log consumption, τ_j is the effect of the j th subject, ε_{ij} is the error term, $i=1, 2, 3, 4$ and $j=1, \dots, n$.

Additionally, all the groups will be compared to assess whether substitutability occurs as a function of different e-cigarette conditions. The relationship between consumption and condition will be modeled according to:

$$y_{ijk} = \mu + \alpha_i * b_j + \tau_k + \varepsilon_{ijk},$$

where y_{ijk} represents the average log consumption by condition for the i th e-cigarette restriction, in the j th smoking status and the k th subject, α_i is the effect of the i th condition on log consumption, b_j is the effect of the j th group on log consumption τ_k is the effect of the k th subject, ε_{ijk} is the error term, $i=1, 2, 3, 4$, $j=1, 2, 3, 4$ and $k=1, \dots, n$.

Additional analyses might be conducted.

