8.0 Procedures Involved

8.1 Describe and explain the study design:

This study uses a mixed design (within-subject repeated measures and between-group). In a one-session survey, participants will complete assessments and purchase tobacco products in a hypothetical ETM. All participants will complete four ETM conditions, all of which include approximately five trials assessing different prices of their preferred

20-008 Effects of Cigarette and E-cigarette flavors on Substitutability in the Experimental Tobacco Marketplace

cigarette. In each ETM condition, participants will purchase tobacco/nicotine products for a 7-day period. Unventilated and ventilated cigarettes, as well as a range of other products (e.g., lozenges, snus, gums, and dip), will always be available. Availability of e-cigarettes will vary according to the experimental conditions:

- A) Nicotine restricted and flavor restricted
- B) Nicotine unrestricted and flavor restricted
- C) Nicotine restricted and flavor unrestricted
- D) Nicotine unrestricted and flavor unrestricted

Participants will be exposed to these conditions across purchasing scenarios in a counterbalanced order.

We will assess these measures in each of four smoker subtypes: unventilated menthol smokers, ventilated menthol smokers, unventilated non-menthol smokers, ventilated non-menthol smokers. For this purpose, ventilated and unventilated cigarettes will be defined as $\geq 20\%$ and $<10\%$ filter ventilation, respectively.

Every participant will complete questionnaires on a computer, tablet or cell phone.

8.2 *Provide a description of:*

- *All research procedures being performed*
- *If the study has more than one procedure, session, and/or subject population, describe each procedure, session, and/or study population separately. For complex studies, you are encouraged to include a figure or chart.*

Participants will complete a one session study including consent and behavioral tasks (ETM and smoking-related assessments).

A Qualtrics survey will administer:

1) the electronic informed consent;

Participants will read through the informed consent and consent will be implied with submission of the assessment at the end of the survey.

2) smoking-related assessments

a) timeline follow back, to assess previous month recent smoking, e-cigarette use and consumption of nicotine products, and to determine ETM budget

b) tobacco use history, exposure and preferences questions;

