c) the Fagerstrom Test of Nicotine Dependence for cigarettes and the Heaviness of Smoking Index for e-cigarettes to assess dependence.

3) the ETM;

Participants will make hypothetical purchases of tobacco products to use throughout the next 7 days. Participants will complete a total of 20 purchasing trials each for 7 days' worth of products. They will be exposed to 4 conditions with their preferred cigarettes increasing in price. The following conditions will be presented in a randomized order:

20-008 Effects of Cigarette and E-cigarette flavors on Substitutability in the Experimental Tobacco Marketplace

Conditions		E-Cigarette	
E-Cigarette	Nicotine restricted	Nicotine unrestricted	
	Flavor restricted	E-cigarette nicotine restricted and E-cigarette flavor restricted	E-cigarette nicotine unrestricted and E-cigarette flavor restricted
	Flavor unrestricted	E-cigarette nicotine restricted and E-cigarette flavor unrestricted	E-cigarette nicotine and unrestricted E-cigarette flavor unrestricted

In the E-Cigarette Flavor Restricted, only tobacco flavors will be available. In the E-Cigarette Flavor Unrestricted, a variety of flavors will be available. In the E-Cigarette Nicotine Restricted, only low nicotine concentration will be available. In the E-Cigarette Nicotine Unrestricted, a variety of nicotine concentration will be available.

A range of other tobacco products will be available across conditions, such as snus, lozenge, gum, and dip.

8.3 Describe:

- *Procedures or safeguards intended to reduce the probability and magnitude of risks. (For example: Reducing the risk of injury in a virtual reality study either by having the subjects sit during the study or by providing an obstacle-free space for walking.)*
- *Be sure to describe all drugs and devices used in the research, when they will be administered or used, and their purpose.*
- *Methods used to collect data about subjects. Please upload all data collection forms to Protocol Management. Some common examples are:*
 - *Screening questionnaires*
 - *Survey(s), including online surveys*
 - *Demographic questionnaire(s)*
 - *Interview guide(s), e.g., questions or pool of questions for semi-structured interviews*
 - *Focus group guide(s)*
 - *Other documents used to collect data*

Participation in this study is completely voluntary and participants may choose not to participate at any time.

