17.0 Risks to Subjects

20-008 Effects of Cigarette and E-cigarette flavors on Substitutability in the Experimental Tobacco Marketplace

17.1 List the reasonably foreseeable risks, discomforts, hazards, or inconveniences to the subjects related to the subjects' participation in the research. Include for the IRB's consideration a description of the probability, magnitude, duration, and reversibility of the risks. Consider physical, psychological, social, legal, privacy, and economic risks. Do not indicate "No risk" or "N/A." Instead, for studies with very low risk (e.g., anonymous online questionnaire on a mundane topic) indicate "The investigators are not aware of any risks from participation in this study." or "No more than risks than are found in everyday life." The example consent form presents a tabular method for risk information, which you can also use here. Common risk types include:

- *Physical (e.g., potential for pain, discomfort, infection)*
- *Psychological (e.g., potential for stress, discomfort, and/or embarrassment)*
- *Social (e.g., potential for discrimination or stigmatization and disruption of personal and family relationships)*
- *Legal (e.g., potential for disclosure of illegal activity, negligence)*
- *Privacy (e.g., potential for personal information being accessed, used, or disclosed without the subjects' knowledge or consent, breach of confidentiality/security)*
- *Economic (e.g., potential for individuals to lose access to economic services, employment, insurability)*

There will be no direct costs for participation, although there are risks.

1. Possible embarrassment: This may result from answering questions that participant considers sensitive. Some of our questions will ask for information about substance use.
2. Possible discomfort: There is also the possibility that participant may become bored or frustrated during the research sessions.
3. Loss of confidentiality: The research team will employ every effort to maintain participant confidentiality, however the loss of confidentiality is a potential risk.

Due to the investigative nature of this study, there may be other risks that are currently unknown.

17.2 Indicate the measures you will use to minimize risks and monitor subjects for safety. (e.g., asking a subject at regular intervals to rate how they are feeling from 1 to 10, or to slowly crouch in order to check their balance.)

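### Condition order is varied within one session, but neither Section 5.2 model has a position term and the order scheme is worded two ways; any drift would go into the residual

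*Combined protocol and SAP*

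**What the plan says.** Section 5.1 sets out a within-subject design: "All participants will complete four ETM conditions, all of which include five trials assessing different prices of their preferred" cigarette. Section 8.2 gives the total: "Participants will complete a total of 20 purchasing trials each for 7 days' worth of products".

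The order of the four conditions is described three times:
- Section 5.1: "Participants will be exposed to these restriction conditions across purchasing scenarios in a counterbalanced order".
- Section 8.1: "Participants will be exposed to these conditions across purchasing scenarios in a counterbalanced order".
- Section 8.2: "The following conditions will be presented in a randomized order".

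No section gives the number of sequences, how participants are allocated to them, or whether they are balanced within the four smoker subtypes.

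Section 5.2 gives two models for average log consumption. In the first, the condition term "is the effect of the i th condition on log consumption", and the rest is defined by "τ_j is the effect of the j th subject, ε_{ij} is the error term". The second crosses condition with smoker group and keeps the subject and error terms. Neither has a term for position, period or sequence. The closing remark that further analyses might be done does not prespecify one. The sample-size calculation in Section 14.1 has no order factor either.

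**The concern.** This is in effect a four-period crossover completed in one sitting. Varying the order is a design measure against change over the session, such as fatigue, learning or loss of interest. Section 17.1 acknowledges the last as a possible discomfort: "There is also the possibility that participant may become bored or frustrated during the research sessions". When order has been controlled by design, the matching analysis normally includes position. Without it, systematic change across positions is treated as random error.

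Two things are at stake. The first is precision: reported standard errors would be larger than they need be, and under balanced orders the tests would reject less often than their nominal level. The second is the order scheme itself. A programmer working from Section 8.2 alone could draw an independent random order for each participant. That does not guarantee that each condition appears equally often in each position, and position balance cannot be added after data collection.

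**Working it through.** **Inputs from the documents.** Four conditions per participant (5.1); 268 completers in total (1.0, 14.1); f=0.24, alpha 0.05, within-subject correlation 0.5, target power 90% (14.1).

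**Assumptions.** The documents give no drift size. I take a linear, additive drift of d residual SDs per position, so the total from first to fourth position is D = 3d, with d from 0.1 to 0.4. I also assume equal subtypes, 268/4 = 67; the documents do not state group sizes.

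**The plan's own figure.** I used the noncentral F for a repeated-measures ANOVA, with noncentrality f² × N × 4/(1 − 0.5). The stated inputs reach 90% power at N=33 for the condition effect, or N=46 for the 4×4 interaction. I could not recover 268. That is a separate matter, but it explains the large power margin at f=0.24.

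**Residual variance with position omitted.** The centred positions are −1.5, −0.5, 0.5 and 1.5, with sum of squares 5. Each subject contributes 3 within-subject df, so the multiplier is 1 + (5/3)d².

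| d | D | Variance multiplier | Reported SE multiplier (square root) | Reported information lost (1 − 1/multiplier) |
|---|---|---|---|---|
| 0.1 | 0.3 | 1.017 | 1.008 | 1.6% |
| 0.2 | 0.6 | 1.067 | 1.033 | 6.3% |
| 0.3 | 0.9 | 1.150 | 1.072 | 13.0% |
| 0.4 | 1.2 | 1.267 | 1.125 | 21.1% |

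**Power for the condition effect in one subtype of 67, position omitted.** The noncentrality is divided by the multiplier. f=0.164 is the effect that 67 participants detect with 90% power when there is no drift.

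| D | Multiplier | Power at f=0.24 | Power at f=0.164 |
|---|---|---|---|
| 0 | 1.00 | 99.9% | 90.0% |
| 0.5 | 1.05 | 99.8% | 88.5% |
| 1 | 1.19 | 99.4% | 83.9% |
| 2 (beyond the assumed range) | 1.74 | 95.3% | 66.3% |

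With a position term, power at f=0.164 stays at 90.0% at every D. With all 268 participants, power at f=0.24 stays above 99.9%.

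**Simulation check** (67 participants, 4,000 runs per setting):

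| Quantity | Four-sequence Williams square | Independent random orders |
|---|---|---|
| Type I error, no position term, D = 0.5 / 1 / 2 | 4.0% / 2.8% / 0.4% | 4.8% / 5.4% / 4.8% |
| Power at f=0.164, D=1, no position term | 85.8% | 83.2% |
| Power at f=0.164, D=1, with position term | 90.5% | 89.0% |

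With the position term, type I error was about 5% under both schemes.

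**Chance imbalance under independent random orders.** The position difference between two conditions has variance 10/3 per person. Its mean over 67 people has SD √(10/(3×67)) = 0.223, so a 95% range of ±0.44 positions. At d=0.3 that shifts a contrast by up to 0.44 × 0.3 = 0.13 residual SD, which is less than one standard error of a two-condition contrast, √(2/67) = 0.17. This shift is already reflected in the enlarged residual, so it is not an additional loss.

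**The case against.** The strongest reply is that nothing in the documents shows an order effect, and that the design already protects the result. With positions balanced, an additive drift cancels from the condition contrasts whether or not it is modelled. The tests then err on the cautious side, and at the planned f=0.24 the loss of power is too small to notice. All of this stands, and it limits the point to precision and specification.

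Four stronger readings are tempting, and the documents do not support them:

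- **The sections contradict each other.** Random allocation of participants to counterbalanced sequences satisfies all three statements. The wording is inconsistent and incomplete, not irreconcilable.
- **The omission biases the contrasts or raises false positives.** Under balance there is no bias from additive drift. Under independent random orders the imbalance is random and type I error stays near 5%.
- **The protocol predicts boredom, so drift is established.** Section 17.1 lists boredom as a possible discomfort. It does not say that purchases change with position. The trials are also not mere repeats, since cigarette price changes within conditions and e-cigarette availability changes between them.
- **The study is underpowered as a result.** At the stated effect size it is not.

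The objection does not explain why a factor controlled by design should be left out of the model when including it costs 3 df. Nor does it settle which scheme will be programmed. The hypothesis in Section 2.2 ranks the conditions, and Section 3.1 asks whether effects differ by subtype. Those contrasts may be smaller than f=0.24, and there precision counts.

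**Conclusion.** The point holds as a low-cost improvement in precision and a gap in specification. It does not threaten validity. Both Section 5.2 models omit position, so any drift across the four conditions would enter the residual. For an assumed 0.1 to 0.4 residual SD per position, residual variance rises by about 1.7% to 27% (6.7% to 15% at 0.2 to 0.3). Under counterbalancing the contrasts are unbiased but the tests conservative, with type I error of 2.8% at 1 SD total drift. Under independent random orders the contrasts themselves lose precision and type I error holds near 5%.

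The practical loss is negligible at f=0.24. It is about six power points at f=0.164 with 1 SD total drift, and under two points when total drift is 0.5 SD or less. These figures rest on linear additive drift of assumed size and on 67 participants per subtype. If there is no drift, nothing is lost.

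**What to change.** 1. State one position-balanced order scheme in the same words in Sections 5.1, 8.1 and 8.2. One example is random allocation to the sequences of a four-sequence Latin or Williams square, balanced as nearly as possible within each smoker subtype. Exact balance is not possible with 67 per subtype (67/4 = 16.75), and near balance is enough. Other balanced schemes would serve equally well.
2. Have the survey software record each participant's sequence.
3. Add position as a fixed effect (3 df) to both models in Section 5.2.
4. Optionally, add a first-order carryover check as a sensitivity analysis.

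The cost is a survey setting, a few sentences of text, and 3 of the (67 − 1) × 3 = 198 within-subject df per subtype. The order scheme has to be settled before data collection. The model term needs only to be written down before the data are analysed.
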